8.1.6 Subject Eligibility

The investigator and/or medically qualified designee will review inclusion and exclusion criteria, medical history, prior medications, etc. to confirm subject eligibility to participate in the clinical trial. This will be documented in the CRF.

To prepare for study participation, subjects will be instructed in the [Lifestyle Considerations](#) of the protocol.

8.2 Visit 2 (Day 1) Baseline/Randomization

Visit 2 may be combined with Visit 1. If Visit 2 is not combined with Visit 1, Visit 2 must occur within 7 calendar days of Visit 1.

8.2.1 Medical History and Prior Medication/Treatment

Review of medication/treatments, all information will be documented in the CRF.

8.2.2 Subject self-assessment

Subjects will be asked to answer the self-assessment questions as per section [Subject Self-Assessment of Signs and Symptoms of Cutaneous and Ocular Irritation](#) prior to randomization and any product application (baseline). Subject responses will be directly entered into the CRF by site staff.

The self-assessment questions will be asked again 1-2 hours following first supervised product use. Subject responses will be directly entered into the CRF by site staff.

If Visit 2 is combined with Visit 1, the initial (baseline) subject self-assessments will be conducted after the initial (baseline) dermatologist and ophthalmologist assessments. These assessments will be conducted prior to the LAST procedure and first product application.

8.2.3 Dermatologist Assessment

A qualified dermatologist will visually assess the subject at Visit 2 (baseline) prior to randomization to determine subject's eligibility to continue in the study. This will ensure the subject is free of any preexisting dermatological pathology prior to using the study products (Edward and Norman, 1982).

Subjects will only be considered eligible to enter the study if they have a dermatologist signs and symptoms cutaneous irritation score of 0.5 (very slight) or greater for erythema and dryness and a score of 0 (none) or 0.5 (very slight) for scaling and edema, as this is representative of the target consumer for the finished product. Subjects presenting with a score of 1 (slight) or greater for edema are excluded from the study as this condition is not reflective of the target population.

Any subject with a score of 3 (severe) in any attribute will exclude the subject from the study, as this condition is not reflective of the target population for the product.

The intensity of any visual signs of dermal irritation will be recorded according to the grade of the reactions per the Dermatological Evaluation ([Safety and Other Assessments](#)). The dermatologist is responsible for grading the level of cutaneous irritation and their opinion on the correct classification of the irritation scores is final. Scores will be directly entered into the CRF.

Any observed cutaneous response that can be denoted according to the grade of the reactions will not be considered an adverse event. Only in the case of unusual reactions will these reactions and the consequences observed upon evaluation be documented as AE's.

If Visit 2 is combined with Visit 1, the initial (baseline) dermatologist assessment will be conducted prior to the LAST procedure. Randomization and initial test product application will occur at least 30 minutes after the LAST procedure.

8.2.4 Ophthalmologist Assessment

A qualified ophthalmologist will assess the subject at Visit 2 (baseline) prior to randomization to determine their subjects to continue in the study. This will ensure the subject is free of any preexisting ophthalmological pathology prior to using the study products (Edward and Norman, 1982). For inclusion into the study each subject should have a total ocular irritation score of 0 (none).

The intensity of any visual signs of ocular irritation will be recorded according to the grade of the reactions according to the Ophthalmological Evaluation ([Safety and Other Assessments](#)). The ophthalmologist is responsible for grading the reactions, their opinion on the classification of the ocular irritation scores is final. Scores will be directly entered into the CRF.

Any observed ocular response that can be denoted according to the grade of the reactions will not be considered an adverse event. Only in the case of unusual reactions will these reactions and the consequences observed upon evaluation be documented as AE's.

If Visit 2 is combined with Visit 1, the initial (baseline) ophthalmologist assessment will be conducted prior to the LAST procedure and any test product application. Randomization and initial test product application will occur at least 30 minutes after the LAST procedure.

8.2.5 Supervised Product Application

Subjects will be asked to answer the self-assessment questions as per section [Subject Self-Assessment of Signs and Symptoms of Cutaneous and Ocular Irritation](#) prior to randomization and any product application (baseline). Subject responses will be directly entered into the CRF by site staff.

The first subject application of the assigned product will be conducted by the subject under the supervision of a trained technician at the study site at Visit 2 (baseline) following completion of the baseline dermatologist and ophthalmologist assessments and the subject self-assessment questions. Subjects will perform a second application of their assigned product at home that evening.

Subjects will then continue to use the product at home, twice a day (morning and evening) during the study period, for a total of 21 (+ 2) days, including the morning of the final visit and will be instructed to contact the study site if they have any reactions.

Sufficient product will be provided to last the duration of the study. Subjects will be dispensed a paper diary alongside their assigned product to be completed at home to record product use.

If Visit 1 and Visit 2 are combined, there should be a minimum of 30 minutes after the LAST has completed before any product application. First application of the assigned product will be conducted by the subject under the supervision of a trained technician at the site following completion of the baseline dermatologist and ophthalmologist assessments and subject self-assessment questions.

The self-assessment questions will be asked again 1-2 hours following first supervised product use. Subject responses will be directly entered into the CRF by site staff.

Spontaneous reporting of AE's and those elicited by asking subjects to respond to a non-leading question such as "How do you feel?" will be assessed and any AEs recorded in the CRF.

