1.2 Schedule of Activities

The schedule of activities table provides an overview of the subject visits and study procedures.

The investigator may schedule visits (unplanned visits) in addition to those listed on the schedule of activities, to conduct evaluations or assessments required to protect the well-being of the subject.

Table 1-1 Schedule of Activities

Procedure/Assessment	Screening	Randomization	Final Visit
	Visit 1 Day - 6 to 0	Visit 2 Baseline/Day 1 ^a	Visit 3 Day 21 (+ 2)
Informed Consent (date and time captured)	X		
Demographics	X		
Medical History	X		
Medications Review (current/concomitant)	X	X	X
Inclusion/Exclusion Criteria	X ^b	X ^c	
Lactic Acid Sting Test (LAST)	X		
Fitzpatrick Skin Type Assessment	X		
Subject Eligibility for Enrolment	X		
Clinical Assessment by Dermatologist		X	X
Clinical Assessment by Ophthalmologist		X	X
Subject Continued Eligibility		X	X
Subject Self-Assessment		X ^d	X
Randomization		X	
Product and Diary Dispensing		X	
Supervised Product Application		X ^e	
Adverse Events (AEs) Review^f	X	X	X
Product and Diary Return (Diary review)			X
Study Conclusion/Subject Exit from Study			X

Footnotes:

- a. Visit 1 and Visit 2 may be combined. If Visit 1 and Visit 2 are not combined, then Visit 2 must occur within 7 calendar days of Visit 1
- b. Inclusion criteria 1-5 and exclusion criteria 1-17 to be assessed at Visit 1
- c. Inclusion criteria 6-10 and exclusion criteria 18-23 to be assessed at Visit 2 (if visit 2 is not combined with visit 1)
- d. Subject self-assessment on Visit 2 will occur prior to randomization and product application (baseline) and 1-2 hours after first supervised product application
- e. If Visit 2 is combined with Visit 1, there should be a minimum of 30 minutes after the LAST has completed before the supervised product application.
- f. Adverse Events (AEs) and therefore all Serious Adverse Events (SAEs) will be collected immediately after a subject provides consent to participate in the study by completing the Informed Consent Form (ICF).

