8.1.5 Lactic Acid Stinging Test (LAST)

Subjects will be instructed to wash their face with room-temperature tap water and to pat dry with paper towels provided by the investigational site. This will ensure a clean surface with which to conduct the LAST.

Approximately 30 minutes after washing, a trained technician will apply an aqueous solution of 10% lactic acid to one nasolabial fold and a saline solution (0.9 Molar) to the other nasolabial fold in the following manner:

The test substances (10% lactic acid; 0.9M NaCl) will be applied concurrently to either the right or the left nasolabial fold. The Sponsor will provide a randomization schedule for the left and right side of the face to have a balanced randomization of the two solutions for the screened subjects.

- A separate swab will be dipped into each test solution (lactic acid and saline solution)
- Each swab will be applied to the upper end of the nasolabial fold and moved in a circular area across the infraorbital part of the cheek under the outer corner of the eye and back along the fold of the nostrils, and along the nasolabial fold to the side of the corner of the mouth, ending at the point where the application started. (See Figure 8-1 as an example).

Figure 8-1

- The complete movement will be repeated once more.
- The applied test substances should not extend beyond this area.
- For each subject, fresh swabs will be used.

Subjects will be asked to report any sensations of discomfort 2-3 minutes and 5-6 minutes after application of the solutions on a 4-point scale (Christensen and Kligman, 1996) per [Table 8-1](#). Scores will be entered into the CRF by a technician.

The test will be suspended after 6 minutes if no local sensation is reported, or immediately upon any reported score of 3. The subjects will be instructed to remove the solutions by thoroughly washing with room-temperature tap water and drying their face with a paper towel.

The sum of the 2-3 and 5-6-minute subject self-assessment scores will be calculated in the CRF for the lactic acid and saline-treated nasolabial folds.

Subjects who report a total score ≥ 2 for the lactic acid-treated site compared to the saline-treated site will be considered to have had a positive response to the LAST. Otherwise, subjects will be considered to have had a negative response to the LAST. Only subjects with a positive response to the LAST will be enrolled into the study.

Table 8-1 Lactic Acid Sting Test Score

Score	Description

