10.4 Reporting Procedures

The investigator and any designees are responsible for detecting, documenting and reporting events that meet the definition of an AE and remain responsible for following up on AEs that are serious, considered related to the study product(s), participation in the study, or a study procedure, or that caused the subject to discontinue the study product or study.

Spontaneous reporting of adverse events and those elicited by asking subjects to respond to non-leading such as "How do you feel" will be assessed and any AE's recorded in the CRF and reported appropriately.

The investigator (or medically qualified designee) is to report all directly observed AEs and all AEs spontaneously reported by the study subject. In addition, each study subject will be questioned about AEs.

Each AE is to be assessed to determine if it meets the criteria for a SAE. If an SAE occurs, expedited reporting will follow local and international regulations, as appropriate.

When an AE occurs, it is the responsibility of the investigator (or medically qualified designee) to review all documentation (e.g. hospital progress notes, laboratory, and diagnostics reports) related to the event.

The investigator or site staff will then record all relevant information regarding an AE in the CRF and all details relating to an SAE in the paper SAE Form provided.

It is **not** acceptable for the investigator (or medically qualified designee) to send photocopies of the subject's medical records to GSK CH in lieu of completion of the AE CRF page/SAE form.

There may be instances when copies of medical records for certain cases are requested by GSK CH. In this instance, all subject identifiers, except for the subject number, will be redacted on the copies of the medical records prior to submission to GSK CH.

The investigator (or medically qualified designee) will attempt to establish a diagnosis of the event based on signs, symptoms, and/or other clinical information. The diagnosis will be the documented as the AE/SAE where known and not the individual signs/symptoms. (e.g. upper respiratory tract infection, seasonal allergy, etc. instead of runny nose).

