10.5 Evaluating Adverse Events

10.5.1 Assessment of Intensity

The investigator or medically qualified designee will make an assessment of intensity for each AE reported during the study and will assign it to one of the following categories:

- Mild: An event that is easily tolerated by the subject, causing minimal discomfort and not interfering with everyday activities.
- Moderate: An event that is sufficiently discomforting to interfere with normal everyday activities
- Severe: An event that prevents normal everyday activities.

NOTE: An AE that is assessed as severe should not be confused with an SAE. Severe is a category utilized for rating the intensity of an event; and both non-serious AEs and SAEs can be assessed as severe. For example, a headache may be severe (interferes significantly with the subject's usual function) but would not be classified as serious unless it met one of the criteria for SAEs, listed above. An event is defined as 'serious' when it meets at least 1 of the predefined outcomes as described in the definition of an SAE, NOT when it is rated as severe.

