10.5.2 Assessment of Causality

The causality assessment is one of the criteria used when determining regulatory reporting requirements.

For each AE (serious and non-serious), the investigator (or medically qualified designee) must provide an assessment of causality on the AE CRF page and the SAE form (subject to the classification of the AE). The investigator will also document in the medical notes that he/she has reviewed the AE and assessed causality, where applicable.

A "reasonable possibility" of a relationship conveys that there are facts, evidence, and/or arguments to suggest a causal relationship, rather than a relationship cannot be ruled out. Generally, the facts (evidence) or arguments to suggest a causal relationship should be provided.

The investigator will use clinical judgment to determine the relationship and will also consult the Safety Statement, in the determination of his/her assessment. Alternative causes, such as

underlying disease(s), concomitant therapy, other risk factors, and the temporal relationship of the event to the study product will be considered and investigated.

For each AE/SAE, the investigator must document in the medical notes that he/she has reviewed the AE/SAE and has provided an assessment of causality.

The investigator's assessment of causality must be provided for all AEs (serious and non-serious); the investigator must record the causal relationship in the CRF, as appropriate, and report such an assessment in accordance with the SAE reporting requirements if applicable.

There may be situations when an SAE has occurred, and the investigator has minimal information to include in the initial report to GSK. However, it is very important that the investigator always make an assessment of causality for every event prior to the initial transmission of the SAE data to GSK CH. The investigator may change his/her opinion of causality in light of follow-up information and send an SAE follow-up report with the updated causality assessment.

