10.6 Follow-up of AEs and SAEs

After the initial AE/SAE report, the investigator is required to proactively follow up with each subject and provide further information on the subject's condition.

All AEs (serious and non-serious) will be followed until resolution, until the condition stabilizes, until the event is otherwise explained, or until the subject is lost to follow-up.

The investigator is obligated to perform or arrange for the conduct of supplemental measurements and/or evaluations as may be indicated or as requested by GSK CH to elucidate as fully as possible the nature and/or causality of the AE. This may include additional laboratory tests or investigations, histopathological examinations, or consultation with other health care professionals.

New or updated information will be recorded on the AE CRF page and on the SAE form (subject to the classification of the AE).

The investigator will submit any updated SAE data to GSK CH within 24 hours of receipt of the information.

Investigators are not obliged to actively seek AEs in former subjects. However, if the investigator learns of a SAE, including death, at any time after a subject has been discharged from the study, and considers the event reasonably related to the study product or study participation, the investigator will promptly notify GSK CH by emailing the information to the GSK CH Clinical Operations Safety Reporting email box (PPD [REDACTED]). The GSK CH Study Manager or designee will be responsible for forwarding the information to the Case Management Group, Global Clinical Safety and Pharmacovigilance group mailbox at GSK (PPD [REDACTED]).

The investigator will submit any updated SAE data to GSK CH within the designated reporting time frames.

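### A subject who leaves the study early because of a local reaction can be missing from the primary and key secondary endpoints, since events are called only at Visit 3 and grading at withdrawal is not required

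*Protocol*

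**What the plan says.** **Event definition.** Protocol 12.3.1 and SAP 4.4.1.1 count a primary event when the total cutaneous score has risen from baseline and the dermatologist calls the change clinically relevant, both at the final visit. Protocol 12.3.2 and SAP 4.5.1.1 do the same for the ophthalmologist. Protocol 9.2.1 and 9.2.2 schedule examiner grading at baseline and the final visit only.

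**Early leavers.** Protocol 7.1 asks for the reason and date of withdrawal, but no grading. A local reaction is not among its mandatory reasons for stopping, although the investigator may withdraw a subject for safety. Protocol 7.2, headed Lost to Follow up, lets the investigator decide whether a returning subject is graded, and says that skipping these procedures is not a deviation provided safety was preserved. Protocol 8.6 allows grading at an AE follow-up visit but does not require it.

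**Analysis.** The Safety population is used. Protocol 12.3.8 and SAP 4.4.3 impute nothing and include dropouts up to discontinuation. SAP 3.4 works by nominal visit. SAP 4.4.1.3 plans no supportive analysis. Neither document states the denominator when the Visit 3 grade is missing.

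**First day.** After the supervised application, the self-assessment questions are "asked again 1-2 hours following first supervised product use. Subject responses will be directly entered into the CRF by site staff" (protocol 8.2.5). Home use starts that evening.

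**The concern.** The subjects most likely to leave early for a product-related reason are those who react. If they go ungraded, they contribute no event to the proportion that is meant to count reactions. The error runs one way: the product looks better tolerated than it is. Protocol section 3 accepts a product when at most 10% of the arm has a reaction judged by the dermatologist. With about 45 to 50 subjects per arm, that rule turns on one or two people.

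**Working it through.** **Inputs.** Acceptance at or below 10% per arm (protocol 3, SAP 1.2). 45 completers per arm, assumed rate 4%, stated probabilities 96.68% and 90.4% (protocol 12.1, SAP 1.4). About 150 randomized so that 135 complete. The documents give no rate of early stopping for a reaction.

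**1. The plan's own figure.** 10% of 45 is 4.5, so at most 4 events pass. P(X ≤ 4 | n = 45, p = 0.04) = 0.9668, and 0.9668³ = 0.9037. Both match the plan. The sample size calculation is not in error.

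**2. Non-completers allowed for.** 150 − 135 = 15, and 15/3 = about 5 per arm.

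**3. Who can go ungraded.**

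| Subject | What the text provides |
|---|---|
| Stops product, stays in study | Visit 3 still applies; a missed assessment is a documented deviation (protocol 9) |
| Failed to return, later contacted | Grading discretionary; omission not a deviation (protocol 7.2) |
| Leaves for any other reason | Reason and date only (protocol 7.1); silent on grading |
| Leaves, but is graded early | No rule says whether a grade taken before Visit 3 can be an event |

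The gap therefore concerns subjects who leave the study.

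**4. Effect on the 10% rule.** The last two columns leave out the ungraded reactors.

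| Treated in arm | True reactors | Ungraded | True rate | Graded subjects as denominator | Safety population as denominator |
|---|---|---|---|---|---|
| 45 | 5 | 1 reactor | 5/45 = 11.1%, fails | 4/44 = 9.1%, passes | 4/45 = 8.9%, passes |
| 50 | 6 | 1 reactor | 6/50 = 12.0%, fails | 5/49 = 10.2%, fails | 5/50 = 10.0%, passes |
| 50 | 6 | 5 subjects, 2 of them reactors | 6/50 = 12.0%, fails | 4/45 = 8.9%, passes | 4/50 = 8.0%, passes |

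In the second row the unstated denominator alone decides the result.

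**5. Illustration under assumed rates.** Take 50 treated per arm, true reaction rate p, and a share s of reactors who leave ungraded. All other subjects are graded. Each subject is independently a graded reactor with probability p(1 − s) or an ungraded reactor with probability ps. The arm passes if events divided by the denominator are at most 0.10. Where two figures are given, the first uses graded subjects and the second the Safety population.

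| p | s = 0 | s = 25% | s = 50% |
|---|---|---|---|
| 4% | 98.6% | 99.1% / 99.6% | 99.8% / over 99.9% |
| 12% | 43.5% | 56.7% / 70.7% | 82.6% / 92.2% |
| 15% | 21.9% | 34.9% / 50.1% | 68.3% / 83.0% |

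The values of s, and the rates above 4%, are assumptions that show the range. At the planning rate of 4% the gap hardly matters. It matters when a product truly exceeds the limit, which is the case the rule exists to catch.

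**The case against.** **The gap is narrower than it may look, and little is hidden.** A reader might infer that grading is optional for anyone who stops product. It is not: a subject who stays in the study keeps Visit 3, and protocol 9 makes a missed assessment a deviation that the sponsor must hear about. The discretionary wording sits under loss to follow-up; for other withdrawals the text is silent rather than permissive. Protocol 8.5 records a primary reason for every early stop, protocol 10.7 separates AE withdrawals from others, and SAP 4.1.1 and 4.6.1 report reasons for discontinuation and AEs leading to it. All of this stands. It confines the point to subjects who leave, and it means the reaction is missing from one proportion rather than from the report. It does not repair that proportion, which is what the 10% rule uses. The AE outputs are also not a sure backstop, because protocol 10.1 keeps an examiner-observed response that the scales can grade out of the AEs unless it is unusual.

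**The first-day self-score.** A reader might also infer that an unreviewed Severe score 1-2 hours after first use is how reactions are lost from the primary endpoint. The documents do not support that link. The score is the subject's own, while the endpoint rests on visually graded erythema, dryness, scaling and edema. Stinging/burning, itching and tightness are not in it.

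Nor does the text leave such a subject without safeguards. An AE enquiry is part of Visit 2, and protocol 10.4 adds: "In addition, each study subject will be questioned about AEs". For AEs, protocol 10.5.1 states: "The investigator or medically qualified designee will make an assessment of intensity for each AE reported during the study". Protocol 10.5.2 adds that "the investigator (or medically qualified designee) must provide an assessment of causality on the AE CRF page", and under 10.6 "the investigator is required to proactively follow up with each subject". Subjects "will be instructed to contact the study site if they have any reactions" (8.2.5), and section 1.2 says: "The investigator may schedule visits (unplanned visits) in addition to those listed on the schedule of activities". A new unfavorable symptom meets the AE definition in 10.1. The exclusion for gradeable responses speaks of observed ones, and protocol 5.8 ties it to the examiners' scales, so a subject-reported sting is not clearly excluded. What stands is only that none of these steps is set off by the score or must be finished before the subject leaves the site.

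The lactic acid test's rule to stop "or immediately upon any reported score of 3" is a weak parallel: it ends a deliberate acid challenge and prescribes no medical review.

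**Conclusion.** The point holds for subjects who leave the study early because of a local reaction. Nothing ensures that they are graded, no rule says that an early grade counts, and nothing is imputed, so they can drop out of the primary and key secondary proportions. For the primary endpoint, one such subject can turn a failing 11.1% into a passing 9.1% or 8.9%. The 10% rule is stated only for the dermatologist's assessment, so for the ocular endpoint the effect is an understated proportion.

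This rests on two assumptions: that the ungraded subject would have been called positive, and that such departures occur at all. The documents give no frequency for either. The plan's allowance of about 5 non-completers per arm shows that there is room for it, not that it will happen. The change is worth making because it is cheap and the bias runs in one direction. The missing score-triggered review on Day 1 is a minor, separate safety point and does not carry this conclusion.

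**What to change.** 1. **Protocol 7.1:** require that any subject who stops product or withdraws early, unless consent is withdrawn, be asked to attend dermatologist and ophthalmologist grading as soon as possible after stopping. Waiting for Visit 3 would let a reaction resolve and then count as a non-event. Subjects who stay in the study also keep Visit 3.
2. **Protocol 7.2:** remove the allowance that omitting this grading is not a deviation.
3. **Protocol 12.3.1 and 12.3.2, SAP 3.4, 4.4.1.1 and 4.5.1.1:** state that a clinically relevant positive at early-stop grading counts as an event, and state the denominator for subjects who remain ungraded.

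**Cost.** Text changes in both documents. At most about 15 extra grading visits by the existing examiners if non-completers match the plan's allowance, plus one for anyone who stops product but stays. Some events will be recorded before Day 21 in an endpoint described as after 21 days of use, so the report should show how many.

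**Optional and separate (protocol 8.2.5).** Have the investigator or an unmasked medically qualified designee review any self-score newly worsened to Severe (3) at 1-2 hours and record a continue/stop decision before the subject leaves. Using someone other than the masked examiners respects protocol 6.5. If all 150 subjects were flagged, at an assumed 5 minutes each, this would take 150 × 5/60 = 12.5 staff hours.
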